#### **9.1.1 Product Characteristics**

Tipifarnib film-coated tablets for oral administration will be supplied in high-density polyethylene bottles. Two strengths (100 mg and 300 mg) of tablets are provided containing either 100 or 300 mg of tipifarnib active substance, respectively. In addition to the active substance, the tablets contain the following inactive ingredients: lactose monohydrate, maize starch, hypromellose, microcrystalline cellulose, crospovidone, colloidal anhydrous silica, and magnesium stearate. The nonfunctional, taste-masking film coatings contain hypromellose, titanium dioxide, lactose monohydrate, polyethylene glycol, and triacetin. Each tablet strength has the same qualitative composition. Further information can be obtained from the current version of the Investigator's Brochure.

#### **9.1.2 Storage and Labeling**

At a minimum, the label of each bottle of tipifarnib tablets shipped to the study sites will provide the following information: batch number/lot number, study identification, required storage conditions, directions for use, and country specific required caution statements (including "New Drug – Limited by United States federal law to investigational use" language).

Tipifarnib accountability records will be maintained by the pharmacy or designated drug preparation area at the study sites. Upon receipt of tipifarnib supplies, the pharmacist or designated study site investigational drug handler will inventory tipifarnib (separately for each strength, if applicable) and complete the designated section of the shipping form. The shipping/inventory form must be sent to Kura Oncology, Inc. or its designee, as instructed.

Tipifarnib should be stored at controlled room temperature 15° to 30° C (59° to 86° F). All study supplies must be kept in a restricted access area.

## **9.2 Treatment Administration**

Tipifarnib will be administered with food at a starting dose of 400 mg, orally, bid on days 1-21 of 28 day treatment cycles. Tipifarnib should be administered orally with a meal in the morning and again with a meal approximately 12 hours later at approximately the same times each treatment day. Subjects should be instructed on the importance of taking their tipifarnib dose with a meal as the presence of food has been shown to improve the absorption of tipifarnib, as well as to reduce variability in the pharmacokinetic profile. Tablets should be swallowed whole with water (~8 oz. or 250 mL) and may be chewed or crushed if the Investigator deems it necessary.

If a dose is vomited or partially vomited it should not be replaced with a new dose. Dosing should resume at the next scheduled dose time.

On Cycle 1 Day 1, the study site will provide tipifarnib to the subject from bulk supplies. Subjects will be provided with diaries with instructions to record the date and time of each dose and asked to bring the diaries and tablet bottles to each clinic visit for subject compliance and drug accountability review by the site staff. For convenience, subjects may receive only one dose (e.g. the evening dose) on Cycle 1 Day 1.

## **9.3 Treatment Assignment**

Treatment will be conducted in an open label manner. Kura Oncology, Inc or its designee will assign a subject number identifier for each subject that is enrolled into the study. Study sites cannot enroll or start dosing the subject without receiving the assigned subject number.

## **9.4 Dose Selection**

Subjects (amendment 3 cohorts 1-4) will receive tipifarnib administered at a dose of 400 mg, orally with food, bid for 21 days in 28 day cycles. This dose regimen was selected based on the average dose intensity for tipifarnib in the INT-17 study that enrolled 252 subjects with relapsed/refractory AML, and the results of the North American Intergroup Phase II study SWOG S0432 that investigated 4 different regimens of tipifarnib in 348 older, previously untreated, AML subjects. The average dose intensity for all treated subjects in INT-17 was 892 mg/day, with a target dose intensity of 900 mg/day (1200 mg/day for 21 days of every 28 day cycle). The average dose intensity for the 'per protocol' INT-17 population was 852 mg/day, equivalent to 567 mg/day bid for 21 days in 28 day cycles. SWOG S0432 randomized AML subjects to receive either 600 mg or 300 mg of tipifarnib orally twice daily on days 1-21 or days 1-7 and 15-21, repeated every 28 days (4 treatment regimens). Responses were seen in all regimens, with overall response rate (CR + CRI + PR) highest (20%) among patients receiving tipifarnib 300 mg twice daily on days 1-21. Fatal toxicity was highest in the 600 mg bid days 1-21 regimen (8%).

[REDACTED]

[REDACTED]

[REDACTED]

[REDACTED]

[REDACTED]

[REDACTED]

[REDACTED]

[REDACTED]

[REDACTED]	[REDACTED]	[REDACTED]
[REDACTED]	[REDACTED]	[REDACTED]
[REDACTED]	[REDACTED]	[REDACTED]

[REDACTED]

[REDACTED]

[REDACTED]

[REDACTED]

[REDACTED]	[REDACTED]	[REDACTED]
[REDACTED]	[REDACTED]	[REDACTED]
[REDACTED]	[REDACTED]	[REDACTED]

[REDACTED]

[REDACTED]

[REDACTED]

[REDACTED]

[REDACTED]

[REDACTED]	[REDACTED]

[REDACTED]

## **9.6 Treatment of Overdose**

An overdose is defined as any dose greater than 30% over the daily tipifarnib dose. Any overdose must be recorded in the study medication and adverse event sections of the CRF. There is no known antidote for tipifarnib. In the event of overdose of tipifarnib, subjects should receive appropriate advice and supportive medical care by the Investigator or his/her designee and be followed-up accordingly.

For monitoring purposes, any case of overdose – whether or not associated with an AE (serious or non-serious) – must be reported to the Sponsor in an expedited manner.

## **9.7 Blinding**

This is an open label study with no placebo or comparators.

## **9.8 Treatment Compliance**

The importance of treatment compliance should be emphasized to the subject. Subjects will be given study drug and detailed instructions on how to take medications at home. Subjects will be instructed to return all used and unused study drug containers at each study visit. Subject compliance with the dosing schedule will be assessed by reconciliation of the used and unused study drug at each clinic visit and review of the dosing diaries. The quantity dispensed, returned, used, lost, etc. must be recorded on the dispensing log provided.

Compliance will be monitored and documented by site personnel on the appropriate form. The site personnel will question the subject regarding adherence to the dosing schedule by reviewing the dosing diaries, recording the number of tablets (and strengths, if applicable) returned, the date returned, and determining treatment compliance (at least 80% of the total assigned dose) before dispensing new medication to the study subject.

## **9.9 Investigational Product Accountability**

The Investigator or designee is responsible for maintaining accurate records (including dates and quantities) of receipt of investigational product (IP), subjects to whom IP is dispensed (subject by subject specific accounting), and loss or accidental or deliberate destruction of IP.

## **9.10 Return and Disposition of Clinical Supplies**

Unused tablets returned by the subject from a prior cycle of treatment may be re-dispensed to the subject. Study drug must be kept in a secure location for accountability and reconciliation by the Sponsor's designated clinical study monitor. The Investigator or designee must provide an explanation for any destroyed or missing study drug or study materials.

Study drug may be destroyed on site, per the site's standard operating procedures, but only after the Sponsor or its designee has been notified and granted approval for drug destruction. All study drug destroyed on site must be documented.

Documentation must be provided to the Sponsor or its designee and retained in the Investigator's study files. If a site is unable to destroy study drug appropriately, the site can return unused study drug to the Sponsor or its designee upon request. The return of study drug or study drug materials must be accounted for on a form provided by the Sponsor or its designee.

All study drug and related materials should be stored, inventoried, reconciled, and destroyed or returned according to applicable state and federal regulations and study procedures.

## **9.11 Prior and Concomitant Medications**

All prescription and over-the-counter medications taken by a subject within 28 days before the first study drug administration will be recorded in the CRF. Any additional concomitant therapy that becomes necessary during the study and any change to concomitant drugs must be recorded in the corresponding section of the CRF, noting the name, dose, duration and indication of each drug.

Supportive care medications, including transfusions and intravenous (IV) hydration, considered necessary for the subject's safety and well-being may be given at the discretion of the Investigator according to local guidelines and standard practices. For concomitant therapy given as a treatment for a new condition or a worsening of an existing condition, the condition must be reported on the AE form of the CRF.

Subjects may use proton pump inhibitors or H2 antagonists during the treatment portion of this study. However, subjects should be instructed to use antacids (magnesium or aluminum containing products) at least 2 hours before or after intake of oral study drug.

## **9.12 Non-permitted Treatments**

Use of the following medications and therapies is not allowed during the study:

- Investigational agents other than tipifarnib.
- Any other anticancer therapy, including radiation or surgery, for the primary disease under study.
- Subjects should not use enzyme-inducing anti-convulsants (e.g. phenytoin, phenobarbital, and carbamazepine) while taking tipifarnib. If needed, subjects may use non-enzyme-inducing anti-convulsants (e.g. gabapentin, topiramate, valproate) while taking tipifarnib.

Any additional concomitant therapy that becomes necessary during the study and any change to concomitant drugs must be recorded in the corresponding section of the CRF, noting the name, dose, duration and indication of each drug.

If the administration of a non-permitted concomitant drug becomes necessary during the study, e.g. because of AEs or disease progression, the subject in question will be withdrawn from the study, and the subject's data obtained before the withdrawal may be used for safety and efficacy evaluations.

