2. Day 25 visit ( $\pm$  5 days) should be performed during Cycles 2, 4, 6, 9 and every approximately 12 weeks thereafter (Cycles 12, 15, etc.) until disease progression.
3. An End of Treatment visit will be conducted within 30 days ( $\pm$  7 days) from the last dose of tipifarnib or immediately before the initiation of any other anticancer therapy.
4. Follow up visit required only for subjects who terminated treatment for reasons other than death or disease progression.
5. Information on subject's survival and use of subsequent anticancer therapy may be collected by phone. Upon disease progression, all subjects will be followed approximately every 12 weeks for survival and the use of subsequent therapy until either death or 12 months after accrual in the subject's study cohort has been completed, whichever occurs first.
6. Medical history is to include demographics, primary diagnosis and WHO classification, outcome and duration of response to prior cancer therapy and any ongoing AEs
7. Assessed throughout the course of the treatment and approximately 30 days after treatment discontinuation. Additional assessments may be performed until AE resolution or the AE is deemed irreversible by the Investigator.
8. Assessment to be performed within 14 days of Cycle 1 Day 1
9. In women with childbearing potential, pregnancy tests (urine or serum) will be conducted at screening (must be performed within 72 hours of Cycle 1 Day 1), on Day 1 of each treatment cycle beginning at Cycle 2 and at the End of Treatment visit. If a positive urine pregnancy test is obtained, a confirmatory serum pregnancy test should be conducted.
10. Assessment to be performed within 72 hours of Cycle 1 Day 1.
11. Assessment to be performed beginning at Cycle 2.

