### **5.1.3 Prior Clinical Experience in CMML**

While there has been no dedicated study of tipifarnib for the treatment of CMML, prior studies of tipifarnib in other hematological malignancies have enrolled CMML patients.

A phase 2 study of tipifarnib was performed in intermediate to high risk MDS in which 82 patients received tipifarnib 300 mg orally bid for the first 21 days of each 28 day cycle. Twenty-six patients (32%) responded to tipifarnib: 12 (15%) CRs and 14 (17%) HIs; 37 patients (45%) had stable disease (modified International Working Group criteria, 2006). Among the 12 CRs, the median response duration was 11.5 months (range, 2.0-21.9 months), the median time to progression was 12.4 months (range, 3.9-23.8 months), and 7 were still alive at time of analysis (all > 3 years). Median overall survival was 11.7 months (95% CI, 9.4-15.0). In the 17 patients with CMML enrolled in this study, 3 patients achieved a CR. Grade 3-4 neutropenia (18%) and thrombocytopenia (32%) were the most common treatment-related adverse events; severe nonhematologic adverse events were rarely reported. In this study, durable responses and acceptable side effects were observed and the authors concluded that tipifarnib is an active agent for the treatment of patients with intermediate to high risk MDS ([Fenaux 2007](#)).

A phase 2, open-label, single-arm, multicenter study was supported by and conducted under the supervision of the United States National Cancer Institute (NCI) Cancer Therapy Evaluation Program (CTEP) and assessed the efficacy and safety of tipifarnib in subjects with previously untreated poor-risk hematologic malignancies (AML, n = 160; high-risk MDS, n = 4; CMML, n = 6). Study subjects received tipifarnib 600 mg orally twice daily for 21 days in 28-day cycles. An overall response rate (CR + PR) of 34% was observed in 148 of 170 patients who were evaluable for response ([Lancet 2004](#)).

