Subjects who terminate treatment for reasons other than death or disease progression will be assessed at regular intervals for disease progression (approximately every 2 months through the first 6 months from the start of the subject's participation in this study and every approximately 12 weeks thereafter) and leukemic transformation (monthly blood counts). Disease assessments performed during the first 9 months from the start of the subject's participation in the study will include bone marrow evaluation. Thereafter, bone marrow evaluations will occur during disease assessments in accordance with institutional standard practice. These assessments will continue until disease progression, withdrawal of subject's consent to study procedures or initiation of another anticancer therapy.

All subjects will be followed-up for safety during treatment and up to approximately 30 days ( $30 \pm 7$  days) after treatment discontinuation or until immediately before the initiation of another anticancer therapy, whichever occurs first. Additional follow up may be implemented until the subject recovers from any emergent treatment related toxicity or the AE is considered irreversible by the Investigator. Target organ toxicities will be monitored via clinical and laboratory assessments using the NCI CTCAE v.4.03 criteria.

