### **8.4 Removal of Subjects from Treatment or Assessment**

Subjects may withdraw their consent to participate in this study at any time without prejudice. The Investigator must withdraw from the study any subject who requests to be withdrawn. A subject's participation in the study may also be discontinued at any time at the discretion of the Investigator and in accordance with his/her clinical judgment. Every effort should be made to complete, whenever possible, the tests and evaluations listed for the End of Treatment visit. The Sponsor must be notified of all subject withdrawals as soon as possible. The Sponsor also reserves the right to discontinue the study at any time for either clinical research or administrative reasons and to discontinue participation by an individual Investigator or site for poor enrollment or noncompliance.

Overall, the reasons for which the Investigator or Kura Oncology may withdraw a subject from study treatment include, but are not limited to, the following:

- Subject experiences disease progression
- Subject experiences unacceptable toxicity
- Subject experiences toxicity that is deemed by the Investigator to be no longer safe for the subject to continue therapy
- Subject requests to withdraw from the study treatment
- Subject requires or has taken medication prohibited by the protocol
- Subject is unwilling or unable to comply with the study requirements
- Subject withdraws consent to collect health information
- Subject was erroneously admitted into the study or does not meet entry criteria
- Subject is lost to follow-up
- Subject becomes pregnant

Subjects will return for an End of Treatment visit within approximately 30 days after the last administration of the study drug (or sooner if another anticancer therapy is to be initiated). If a subject fails to return for scheduled visits, a documented effort must be made to determine the reason. If the subject cannot be reached by telephone after 2 attempts, a certified letter should be sent to the subject (or the subject's legally authorized representative, if appropriate) requesting contact with the Investigator. This information should be recorded in the study records.

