### **11.7.2 Follow Up after Disease Progression**

Upon disease progression, all subjects in the study will be followed approximately every 12 weeks for survival and the use of subsequent therapy until either death or 12 months after accrual of the study cohort has been completed, whichever occurs first. Information on survival and subsequent anticancer therapy may be collected by phone.

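### Protocol 9.12 takes a subject who needs a non-permitted drug off the study, in tension with 8.4 and 11.7.2; applied literally, it could bias 1-year survival by an amount and in a direction the documents do not fix

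*Protocol*

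**What the plan says.** **Protocol 9.12** lists treatments not allowed during the study. The list includes any other anticancer therapy for the disease under study. If such a concomitant drug becomes necessary, "e.g. because of AEs or disease progression, the subject in question will be withdrawn from the study". This withdrawal is mandatory and at study level. On the use of data, the same sentence mentions only what was collected earlier: "data obtained before the withdrawal may be used for safety and efficacy evaluations".

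**Protocol 8.4** gives reasons for which the investigator or sponsor "may withdraw a subject from study treatment include, but are not limited to, the following". One of them is "Subject requires or has taken medication prohibited by the protocol". This is the same trigger, but the action is discretionary and is framed as leaving treatment.

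**Protocol 11.7.2** says that after progression "all subjects in the study will be followed approximately every 12 weeks for survival and the use of subsequent therapy", until death or 12 months after cohort accrual ends. Section 8.1 and SAP 5.2 repeat this. Table 1 footnote 5 adds that "Information on subject's survival and use of subsequent anticancer therapy may be collected by phone". For subjects who stop treatment without progression, section 8.1 ends disease assessments at progression, withdrawal of consent "or initiation of another anticancer therapy". No such stop is set for survival follow-up.

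**SAP 10.3.4** estimates 1-year survival by Kaplan-Meier and censors at the date last known alive. It has no rule for subjects withdrawn under 9.12. SAP 8 lists progression among the reasons for early study discontinuation, so the SAP does not settle the matter.

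**The concern.** A site reading 9.12 alone could close a subject's participation when next-line therapy starts and make no further survival contacts. Progression is one of 9.12's own examples, and other anticancer therapy is on its list, so the case need not be rare.

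Those subjects would be censored for overall survival around progression. Kaplan-Meier assumes that a censored subject has the same future risk as the subjects still under observation at that time. That is doubtful when censoring follows progression and a decision to treat. The estimate at stake is 1-year survival, a secondary endpoint. Survival contacts that are not made may not be recoverable later.

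ORR and the two-stage decisions are not at stake, because responses recorded before withdrawal are kept. Duration of response and PFS are already censored before subsequent anticancer therapy (SAP 10.3.2 and 10.3.3).

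**Working it through.** **1. Text.** The provisions side by side:

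| Source | Trigger | Consequence |
|---|---|---|
| Protocol 9.12 | Non-permitted drug needed (AE or progression as examples) | Mandatory exit from the study; earlier data usable |
| Protocol 8.4 | Prohibited medication needed or taken | May be taken off study treatment |
| Protocol 8.1, 11.7.2, Table 1 fn. 5; SAP 5.2 | Progression | Survival and subsequent therapy followed in all subjects |

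Recording subsequent therapy makes sense only if starting it does not end follow-up. Continued follow-up is therefore the evident intent, and 9.12 is the text out of line.

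**2. Illustration of the bias.** The plan gives no 1-year survival figure to reproduce. It also gives no withdrawal share, PFS or post-progression survival for this trial, so all of these are assumptions. The one anchor is an earlier MDS study, where "Median overall survival was 11.7 months" (Protocol 5.1.3). With exponential survival that is exp(-ln 2 × 12/11.7) = 0.49 at one year.

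Let λ = ln 2 / median PFS. Assume 80% of first events are progression and 20% death, exponential survival with mean μ after progression, and a random share q of progressing subjects censored at progression.

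- Alive without progression: P0(t) = exp(-λt)
- Alive after progression: P1(t) = 0.8λ[exp(-t/μ) - exp(-λt)]/(λ - 1/μ)
- True 1-year survival: P0(12) + P1(12)
- Death rate among those still observed: h(t) = [0.2λP0 + (1-q)P1/μ] / [P0 + (1-q)P1]
- Large-sample Kaplan-Meier value: exp(-∫h dt) from 0 to 12 months

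Example with median PFS 4 and μ = 6 months: λ = 0.1733, P0(12) = 0.125, and P1(12) = 0.1386 × (0.1353 - 0.1250)/0.00662 = 0.216, so true survival is 0.341. The Kaplan-Meier value is 0.354 at q = 10% (+1.2 points) and 0.376 at q = 25% (+3.4 points).

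| Median PFS, μ (months) | True 1-year survival | q = 10% | q = 25% |
|---|---|---|---|
| 4, 6 | 34% | +1.2 | +3.4 |
| 4, 9 | 43% | +0.9 | +2.5 |
| 4, 11.5 (median OS 11.7) | 49% | +0.7 | +1.9 |
| 6, 7.1 (median OS 11.7) | 49% | +1.4 | +3.9 |

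Variations:

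- Censoring two months after progression gives +0.4 to +0.9 at 10% and +1.2 to +2.3 at 25%.
- At median OS 11.7 months, 90% progression or a median PFS of 8 months gives +1.1 to +2.4 at 10% and +3.2 to +6.5 at 25%.
- At q = 50% the four scenarios give about +4.5 to +9.

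**3. Does the sign hold?** The table assumes that withdrawn and retained subjects fare alike after progression and that death rates rise at progression. These runs relax that:

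- *Fitter subjects withdrawn, same model.* With median PFS 4 and mean post-progression survival of 16 months if withdrawn and 8 if retained: -0.5 at 10% and -1.1 at 25%. With median PFS 6 and means of 10 and 5: +0.5 and +1.5.
- *Three-state model set to 49% true survival, median time to progression 4 to 12 months.* If the death rate does not change at progression, the bias is 0. If the rate is 4 times higher after progression for everyone, it is +1.9 to +2.3 at a 20% share and +11.3 to +14.5 at 80%. If it is 2 times higher in the withdrawn and 4 times in the retained, it is -2.0 to +4.7 over shares of 10% to 80%. At 1 and 4 times, it is -8.7 to -0.5.

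**4. Scale.** The binomial 95% half-width at 49% with 18 subjects is 1.96 × √(0.49 × 0.51/18) = 0.231, or about 23 points.

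**The case against.** The best defence is that the documents largely settle the intent. Survival follow-up of all subjects after progression is stated several times, and the SAP censors PFS and duration of response at subsequent therapy but sets no such rule for overall survival. Section 9.12 speaks of a concomitant drug, which may mean one taken alongside tipifarnib, and SAP 9.2 and 9.3 handle concomitant medication and subsequent anticancer therapy separately. On that narrow reading next-line therapy falls outside 9.12 and few subjects are affected. The list in 8.4 is also permissive and mixes exits from treatment with exits from the study, such as loss to follow-up. It does not say that treatment alone stops, so 8.4 and 9.12 differ in scope rather than flatly contradict each other. Nor does allowing use of earlier data expressly bar later survival data.

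Most of this stands, and it is why the point is minor. It does not remove the problem. Within 9.12 only the anticonvulsant item is tied to time on tipifarnib; the list as a whole applies during the study, and progression is a named trigger. A site following the sentence literally would stop contacts that the sponsor wants.

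A reader might go further and infer that 9.12 makes 1-year survival slightly too high. The documents do not support that. The direction depends on who is withdrawn, and the trigger is not random: subjects who can take next-line therapy may be the fitter ones. "Slightly" depends on a share that the documents do not give.

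**Conclusion.** The inconsistency is real. Section 9.12 prescribes study-level withdrawal for a trigger that 8.4 places under study treatment, and this cuts across the planned survival follow-up. Applied literally, it makes censoring for 1-year survival related to prognosis.

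The effect cannot be sized or signed from the documents:

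- Zero if sites follow 11.7.2.
- Upward if withdrawn subjects have the same or worse post-progression survival as those retained and die faster than before progression: about 1 to 4 points at 10% to 25% of progressing subjects in the four main scenarios, up to 6.5 in the sensitivity runs, and more at larger shares.
- Possibly downward if those withdrawn for next-line therapy are fitter.

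All figures rest on assumed withdrawal shares, PFS and post-progression survival. In the main scenarios the bias is small beside a sampling half-width of about 23 points for an 18-subject cohort. ORR and the two-stage decisions are unaffected. Severity: minor.

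**What to change.** In Protocol 9.12, replace withdrawal from the study with withdrawal from study treatment, to agree with 8.4. Add that follow-up under 11.7, including survival follow-up, continues unless the subject withdraws consent, and that these data are used for overall survival.

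The cost is one protocol sentence, or a memo to sites until the next amendment. No visits are added, because the 12-weekly contacts are already planned and may be made by phone. In the models above, continued follow-up brings this source of bias to zero whatever the withdrawn subjects' prognosis.
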